7.8.4 Daily Nasal Peak Inspiratory Flow (at Home)

All patients will be asked to perform nasal peak inspiratory flow (NPIF) testing at home BID and to record the results using the patient diary dispensed at Visit 1.

7.8.5 Computed Tomography (CT) Scan

Sinus CT scanning is used to assess fluid-filled or thick-membraned sinuses, to assess the extent of inflammation, to assess polyps and other growths in the airway, and to create a “map” of the patient’s sinus cavities. An Imaging Manual will be provided separately to Study Sites that are approved and qualified to perform CT Scans. The Imaging manual will detail the equipment settings and requirements for scanning. The Imaging Manual will also detail the radiologic scoring of CT scans. All scans will be reviewed by blinded central over-read. Lund-Mackay Computed Tomography qualitative scores and quantitative analysis will be performed from patients enrolled at Study Sites that are approved and qualified to perform CT scans.

7.8.6 In-Clinic Pulmonary Function Tests (PFT)

Spirometry is required for only patients with comorbid asthma (i.e. demonstrating $\geq 12\%$ reversibility at screening or in the 12 months prior). Spirometry (peak expiratory flow, forced vital capacity, and FEV₁) will be performed according to American Thoracic Society and the European Respiratory Society (ATS/ERS) Standardization of Spirometry (2019), with equipment operated by trained clinical staff.

Pulmonary function will be assessed in clinic or by home healthcare at the timepoints indicated in the Schedule of Assessment ([Table 1](#)).

7.8.7 Smell Test (UPSTIT)

The UPSIT is a commercially available, validated smell test that has 40 items, where each item has 1 correct answer and 3 incorrect answers or “distractors”. The test is a forced choice paradigm, that is, if an individual is unsure of an answer, they are forced to guess a response hence a score of 25% on average would reflect random guessing. An UPSIT result is scored out of 40 where a higher score indicates better olfaction. The test consists of 4 different 10-page booklets, with a total of 40 questions. On each page, there is a different “scratch and sniff” strip which is embedded with a microencapsulated odorant. There is also a 4-choice multiple choice question on each page. The scents are released using a pencil. After each scent is released, the patient smells the level and detects the odor from the 4 choices. There is an answer column on the back of the test booklet, and the test is scored out of 40 items. The score is compared with scores in a normative database from 4000 normal individuals, this tells the level of absolute smell function. The score also indicates how the patient does in accordance to their age group and sex.

The test is occasionally judged to have an American cultural bias. There have been British, Chinese, French, German, Italian, Korean and Spanish UPSIT versions made which may be used depending on the countries in which the study is performed.

For the timepoints on which the UPSIT is administered, refer to the Schedule of Assessments ([Table 1](#)).

7.8.8 Visual Analog Scale for Rhinosinusitis (VAS-RS)

The Visual Analogue Scale for rhinosinusitis (VAS-RS) is a 10 cm scale that ranges from “no symptoms” to “worst symptoms ever” for each of the nasal symptoms (Appendix A). The VAS will direct the patient to mark a vertical line at the point that best corresponds to how bothersome their symptoms have been between visits the VAS-RS is collected.

For the timepoints on which the VAS-RS is assessed, refer to the Schedule of Assessments ([Table 1](#)).

7.8.9 Total Nasal Symptom Score (TNSS)

The Total Nasal Symptom Score (TNSS) is the sum of scores for each of nasal obstruction, nasal itching/sneezing, and Secretion/Runny nose (rhinorrhea), using a 4-point scale (0, 1, 2, 3), where 0 indicates no symptoms, a score of 1 for mild symptoms that are easily tolerated, 2 for awareness of symptoms which are bothersome but tolerable and 3 is reserved for severe symptoms that are hard to tolerate and interfere with daily activity (Appendix B). TNSS is calculated by adding the score for each of the symptoms to a total score out of 9.

For the timepoints on which the TNSS is assessed, refer to the Schedule of Assessments ([Table 1](#)).

7.8.10 Sino-Nasal Outcome Test (SNOT-22)

The Sino-Nasal Outcome Test (SNOT-22) is a 22-item list of symptoms and social/emotional consequences related to the patient’s rhinosinusitis, using a 5-point scale (0,1,2,3,4,5), where score of 0 indicates No Problem, 2 for Very Mild Problem, 3 for Mild or Slight Problem, 4 for Moderate Problem, and 5 for Problem as bad as it can be. Patients will also be asked to mark the most important items that affect their health for a maximum of 5 out of the 22 items listed during the reporting period (Appendix C). A Minimal Clinically Important Difference (MCID) value for SNOT-22 total scores is defined as improvement of at least 8.9 points in patients with chronic rhinosinusitis (Hopkins C 2009). For the timepoints on which the SNOT-22 is assessed, refer to the Schedule of Assessments ([Table 1](#)).

7.8.11 EuroQoL Health Status Questionnaire (EQ-5D-5L)

The EuroQoL Health Status Measure, 5 Dimensions/5 Levels (EQ-5D-5L) is a well-validated, general health-related quality of life assessment tool published by the EuroQoL Group. The EQ-5D-5L consists of 2 pages: the EQ-5D descriptive system and the EQ visual analogue scale (EQ-VAS). The descriptive system comprises 5 dimensions: mobility, self-care, usual activities, pain/discomfort and anxiety/depression. Each dimension has 5 levels: no problems, slight problems, moderate problems,

severe problems and extreme problems. The patient is asked to indicate their health state by choosing the most appropriate statement in each of the 5 dimensions. This decision results in a 1-digit number that expresses the level selected for that dimension. The digits for the 5 dimensions can be combined into a 5-digit number that describes the patient's health state. The EQ-VAS records the patient's self-rated health on a vertical visual analogue scale, where the endpoints are labelled 'The best health you can imagine' and 'The worst health you can imagine'. For the timepoints on which this questionnaire is administered, refer to the Schedule of Assessments ([Table 1](#)).

7.8.12 Healthcare Resource Utilization Questionnaire

The Healthcare Resource Utilization Questionnaire will be used to evaluate the patients' need for medical services related to symptoms of their chronic rhinosinusitis with nasal polyposis. This questionnaire will be completed by patients. For the timepoints on which this questionnaire is administered, refer to the Schedule of Assessments ([Table 1](#)).

7.8.13 Pharmacodynamic Endpoints

Blood will be collected from patients throughout the study as indicated in the Schedule of Assessments ([Table 1](#)), for measurement of biomarkers of inflammation associated with chronic rhinosinusitis with nasal polyposis.

7.8.14 Pharmacokinetic Assessments

Whole blood for plasma CBP-201 concentrations will be obtained at the following visits to characterize the PK of the drug at steady-state and to characterize the return to baseline after treatment stops.

7.8.15 Blood Volumes

The approximate blood volumes to be collected for safety laboratory tests, pregnancy test, PK, and PD are given in Table 3. These volumes may vary slightly based on regional differences in standard tube sizes. The total sample volumes over the course of the 32-week study will not exceed a safe and medically advisable amount in any given collection event.

Table 3 Blood Volumes

Assessment		Sample Volume (mL)	No. of Samples	Total Volume (mL)
Safety	Hematology	3	11	33
	Biochemistry	7.5	11	82.5
Human immunodeficiency virus/hepatitis B surface antigen test		4	1	4
Pregnancy		5-7	1	5-7

Assessment	Sample Volume (mL)	No. of Samples	Total Volume (mL)
Pharmacokinetics	5-7	7	35-49
Pharmacodynamics	5-7	6	30-42
Antidrug antibody/ neutralizing antibody	3-5	5	15-25

8 REPORTING ADVERSE EVENTS

8.1 Definitions

8.1.1 Adverse Event

An AE is defined as any untoward medical occurrence in a patient during a clinical study, whether or not it is related to the IP, at any time after the patient signs the ICF until Visit 17 (End of Study) or an Early Termination Visit, whichever occurs first.

8.1.2 Serious Adverse Event

An AE is considered “serious” if it:

- Results in death
- Is life-threatening: when the patient is, in the opinion of the Investigator, at immediate risk of death from the event as it occurs. This definition does not include an event that hypothetically might have caused death if it were more severe
- Requires hospitalization or prolongation of existing hospitalization
- Results in persistent or significant disability or incapacity (ie, substantial disruption of a person’s ability to conduct normal life functions)
- Consists of a congenital anomaly or birth defect in the offspring of a patient
- Is a medically important event, based upon the medical judgment of the Investigator, that may jeopardize the patient and may require medical or surgical intervention to prevent one of the outcomes listed above

Hospitalization is defined as any initial admission (even less than 24 hours) in a hospital or equivalent healthcare facility. An emergency room visit does not necessarily constitute a hospitalization, however, the event leading to the emergency room visit is assessed for medical importance. Hospitalization in the absence of a precipitating clinical AE is not itself an SAE. Examples include optional admission for elective surgery, administrative admission (for a yearly physical or regular diagnostic procedure not associated with an AE), or admission for treatment of a pre-existing condition not associated with the development of a new AE or the worsening of a pre-existing condition.

8.2 Eliciting Adverse Event Information

The period of observation for AEs and SAEs extends from the time the patient signs the ICF until exit from the study. At each study visit patients will be asked a standard question to elicit any medically related changes in their well-being. They will also be asked if they have been hospitalized, had any accidents, used any new medications, or changed concomitant medication regimens (both prescription and over-the-counter medications).

In addition to patient observations, AEs will be documented from any data collected on the source document and eCRF (eg, laboratory values, physical examination findings, medical history, ECG changes), or other documents (eg, patient diaries) that are relevant to patient safety. Adverse medical conditions present at Baseline or since last assessment which become worse following exposure to study drug should be considered AEs. Any laboratory values that emerge or worsen since the last laboratory assessment and are deemed clinically significant by the Investigator should be considered AEs.

8.3 Adverse Event Reporting

Both AEs and SAEs will be recorded from the time the patient signs the ICF until Visit 17 or Early Termination Visit, whichever occurs first. All AEs must be fully recorded into the source documents throughout the entire study period and will be transcribed into the AE eCRF, whether or not they are considered to be drug related.

If a diagnosis could be established, record the diagnosis as AE; If impossible to establish a diagnosis, record Signs and symptoms as AEs until a diagnosis could finally be determined, information including signs and symptoms of each AE should be described in detail, including

- Onset time and date
- Offset time and date
- Severity (mild, moderate, severe, life-threatening, death)
- Relationship to study drug (related, not related),
- Action taken with study drug (dose not changed, study drug interrupted, study drug withdrawn, not applicable, unknown)
- Outcome (recovered/resolved, recovering/resolving, not recovered/not resolved, resolved with sequelae, fatal, unknown)

Adverse events should be followed until the event is resolved and/or stabilized whether or not the event is considered related to study drug. Adverse events resulting from concurrent illnesses, reactions to concurrent illnesses, reactions to concurrent medications, or progression of disease states must also be reported. All AEs will be followed to adequate resolution. Medical Dictionary for Regulatory Activities (MedDRA) will be used to code AEs and medical history. In addition, the World Health Organization Drug Dictionary (WHODrug) will be used to code medication usage.

Any medical condition that is present at the time the patient is screened but does not deteriorate should not be reported as an AE. However, if it deteriorates at any time during the study, it should be recorded as an AE.

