5.6 Rhinosinusitis or Asthma Exacerbation as Withdrawal Criterion

If there are safety concerns, the Investigator may, but is not required to, discontinue the patient's study drug treatment for lack of efficacy if the patient experiences a rhinosinusitis exacerbation that results in 1 or more of the following:

- Hospitalization due to rhinosinusitis
OR
- Treatment with systemic steroids for > 5 days
OR
- Decision to proceed to surgery for removal of nasal polyps.

The Investigator may, but is not required to, discontinue the patient's study drug treatment for lack of efficacy if the patient experiences an asthma exacerbation as defined as a deterioration of asthma that results in 1 of the following:

- Asthma requiring prolonged treatment increase of approximately 4 times the baseline dose of ICS or the physician-prescribed addition of additional controllers
OR
- Hospitalization due to asthma

Even if the patient's study drug treatment is discontinued due to treatment failure, the patient should be encouraged to remain in the study and all study procedures should be completed unless the patient withdraws consent or is lost to follow-up.

Note: Patients may experience symptoms of decreased asthma control that do not reach the level of the exacerbation criteria but warrant concern from the clinical site. These "loss of control events" are defined as follows: An increase of 6 or more reliever occasions (1 puff = reliever occasion) in a 24-hour period for ≥ 2 consecutive days along with decreased peak flow will fulfill the definition of "loss of asthma control." Loss of asthma control events should be flagged in the eCRF and may be further recorded as an AE (worsening of specific symptoms). Patients experiencing a loss of asthma control may remain in the study but the patient should be instructed to contact the site for management of symptoms.

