#### 4.12.2 Adverse Events

Adverse events will be coded using the Medical Dictionary for Regulatory Activities (MedDRA) Version 24.0. Severity and causality of AE will be evaluated by the investigator. Severity of AE will be graded according to the Common Terminology Criteria for Adverse Events (CTCAE), version 5.0. Incomplete start and end date of the AE will be imputed as described in **Error! Reference source not found.**

Subjects with multiple incidents of events for a given preferred term (PT) and system organ class (SOC) will be counted only once. Similarly, if a subject experiences multiple incident of events for a given PT and SOC, the worst severity will be used in the summaries presenting severity, and the worst causality to study drug will be used in the summaries presenting causality, respectively.

Any missing severity will be queried for completion. If the severity is still missing in the final data and the outcome of AE is death, then it will be deemed as Grade 5, and if the life-threatening is marked, then it will be deemed as Grade 4. Otherwise, the severity still missing in the final data will be deemed as Grade 3.

Any missing causality will also be queried for completion, and any events that still have missing causality in the final data will be deemed as 'Related'.

The imputed severity and relationship will be used in table summary, but the original value will be maintained as missing in the by-subject listing.

Adverse event summaries will be sorted in terms of decreasing frequency for SOC, and PT within SOC, in the overall group, and then alphabetically for SOC, and PT within SOC if there are any ties in frequency.

An overall summary of AEs will include the number and percentage of subjects in the following categories:

- Any AEs
- AEs by maximum severity
- Any AEs related to study drug
- Any AEs related to study procedure
- Any AEs occurring more than 5% of subjects in overall
- Any serious AEs
- Any AEs leading to death
- Any AEs leading to study drug discontinuation
- Any AEs leading to study drug interruption
- Any TEAEs
- TEAEs by maximum severity
- Any TEAEs related to study drug
- Any TEAEs related to study procedure
- Any TEAEs occurring more than 5% of subjects in overall
- Any serious TEAEs

- Any TEAEs leading to death
- Any TEAEs leading to study drug discontinuation
- Any TEAEs leading to study drug interruption

Summaries of following AEs including the number and percentage of subjects will also be provided:

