- AEs by SOC and PT
- Serious AEs by SOC and PT
- TEAEs by SOC and PT
- TEAEs by SOC and PT for Subjects with Rescue Medications
- TEAEs by decreasing frequency of PT
- TEAEs by SOC, PT, and maximum severity
- TEAEs of grade 3 or higher by SOC and PT
- TEAEs related to study drug by SOC and PT
- TEAEs related to study procedure by SOC and PT
- Any TEAEs occurring more than 5% of subjects in overall
- Serious TEAEs by SOC and PT
- TEAEs leading to death by SOC and PT
- TEAEs leading to study drug discontinuation by SOC and PT
- TEAEs leading to study drug interruption by SOC and PT

By-subject listings of corresponding adverse events summary will also be provided.

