#### 4.12.3 Adverse Event of Special Interest

The TEAEs of special interests are defined as:

- Conjunctivitis
- Keratitis
- Anaphylaxis
- Parasitic and opportunistic infections
- Pregnancy
- Symptomatic overdose
- Injection site reactions lasting longer than 24 hours
- AST/ALT elevated > 5X ULN

The TEAEs of special interests will be summarized using frequencies and percentages by SOC and PT. Further analysis on AESI will also be summarized including the risk difference, its 95% confidence interval, and p-value using CMH test stratified by presence of comorbid asthma if there are at least 4 subjects in any treatment arm. The risk difference will be computed as each CBP-201 treatment group versus placebo. The confidence intervals and p-values will not be adjusted for

multiplicity so should be considered accordingly. By-subject listings will also be provided for all AESIS.

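### AE entry is optional for sub-exacerbation loss-of-asthma-control events (Protocol 5.6, against 8.2 and 8.3), and no SAP output uses the eCRF flag that stands in for it

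*Protocol*

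**What the plan says.** Two general rules stand in the adverse event chapter of the protocol. Section 8.2 states: "Adverse medical conditions present at Baseline or since last assessment which become worse following exposure to study drug should be considered AEs". Section 8.3 says that a condition present at screening is not an AE while it stays stable, but "if it deteriorates at any time during the study, it should be recorded as an AE". Neither section makes an exception for asthma.

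A specific rule stands in a note to Protocol 5.6, the section on exacerbations as withdrawal criteria. It concerns "symptoms of decreased asthma control that do not reach the level of the exacerbation criteria". It defines loss of asthma control as an increase of at least 6 reliever occasions in 24 hours, on at least 2 consecutive days, together with decreased peak flow. For these events it says: "Loss of asthma control events should be flagged in the eCRF and may be further recorded as an AE (worsening of specific symptoms". So the flag is a *should* and the AE entry is a *may*.

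SAP 4.12.2 introduces its main table with "An overall summary of AEs will include the number and percentage of subjects in the following categories", and goes on to tables such as "TEAEs by SOC and PT". SAP 4.12.3 opens its list with "The TEAEs of special interests are defined as" and names eight items, none of them an asthma event. SAP 4.15 records the early termination and moves the focus of the analysis to safety.

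**The concern.** Loss of asthma control, as 5.6 defines it, is a worsening of a condition the patient already had. Under 8.2 and 8.3 it should be an AE; under 5.6 it need not be. A site that reads the specific note can flag the event and stop there. A site that reads the AE chapter enters an AE. Each can claim to have followed the protocol.

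This would be harmless if the flag fed an output. It does not, so a flagged event without an AE entry reaches no table or listing. It also need not receive a causality assessment (Protocol 8.4) or a severity grade (8.5), since both attach to AEs.

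At stake is consistent ascertainment of milder asthma events in a trial that deliberately enrolled many patients with asthma and whose final analysis now centres on safety. With small arms, a few events recorded at some sites and not at others can change what a table shows.

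**Working it through.** The protocol and SAP state no figure on this point, so the main check compares the texts.

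**Step 1. Which events does the optional wording cover?**

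| Asthma event | Governing text | AE entry |
|---|---|---|
| Below the exacerbation criteria, meeting the loss-of-control definition | Protocol 5.6 note, and also 8.2 and 8.3 | *may* (5.6) against *should* (8.2, 8.3) |
| Exacerbation as defined in 5.6 | 8.2 and 8.3; the note does not apply | *should* |
| Hospitalisation for worsening asthma | 8.1.2 | SAE |

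The conflict is confined to the first row.

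**Step 2. Could a flagged event without an AE entry appear anywhere in the SAP?**

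- 4.12.2: all summaries and listings are built from AEs and TEAEs. The table for patients with rescue medication is also a TEAE table.
- 4.12.3: the eight AESIs include no asthma event and are themselves TEAEs.
- 4.11.3.2: the definition of rescue medication covers sinonasal treatment, systemic corticosteroids and surgery. It includes neither short-acting reliever use nor an increase in inhaled corticosteroid.
- 4.13.4: every healthcare-use item concerns nasal polyps.
- 4.11.5 and 4.15: FEV1 is an exploratory efficacy endpoint and is now listed only.
- 4.9: added reliever or controller drugs may show in the concomitant medication summary, but that does not identify the event.
- The SAP mentions neither the flag nor diary puff counts.

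Such an event therefore appears in no planned safety output.

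**Step 3. How many patients fall under the rule?** Planned total: 147. The cap on patients without asthma is about 70 in Protocol 9.1 and SAP 4.14, and about 66 in Protocol 5.3.

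- 147 − 70 = 77; 77/147 = 52%; 77/3 = 25.7 per arm
- 147 − 66 = 81; 81/147 = 55%; 81/3 = 27 per arm

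**Step 4. Illustration only.** The documents give no event rate. Assume that between 5% and 30% of 26 patients with asthma per arm have at least one such event:

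- 26 × 0.05 = 1.3 patients per arm
- 26 × 0.30 = 7.8 patients per arm

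Of these, anything from all to none could be visible in the AE tables, depending on how sites use the discretion. The figures use planned enrolment. Actual enrolment was cut short and is not stated, so they do not describe the data that will be analysed.

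**The case against.** The strongest reply is that the note in 5.6 sits in a section on withdrawal and grants no exemption from the AE chapter. Section 8.2 already names patient diaries as a source of AEs, so a site applying 8.2 and 8.3 would record the event. This stands in part. It means that loss is possible and not shown. It does not remove the discretion, because a site can also follow 5.6 to the letter and enter nothing.

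Three stronger readings are tempting, and the documents do not support them.

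- *Asthma worsening in general can vanish from the safety results.* Step 1 above shows otherwise: only events below the exacerbation criteria are affected.
- *Section 8.3 makes every disease progression reportable.* The words "progression of disease states must also be reported" invite this, but the subject of that sentence is adverse events that result from progression. The argument rests on the deterioration rule in 8.3 and on 8.2.
- *Incidence is understated, or tilted towards one arm.* Neither is shown. The trial is double-blind (Protocol 5.4), so discretion should not systematically favour an arm. The main exposure is the absolute incidence and its consistency between sites.

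Two further objections hold as limits. The definition of loss of control gives no cut-off for decreased peak flow. The home measurement described in Protocol 7.8.4 is nasal inspiratory flow, while peak expiratory flow comes with scheduled spirometry (7.8.6). A table of the flag inherits that softness. Also, the eCRF and the Data Management Plan are not among the documents, so an automatic query from flag to AE may already exist.

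Finally, requiring AE entry is not neutral. Protocol 5.7 and 8.7 attach mandatory discontinuation of study drug to related respiratory TEAEs of grade 2 or higher, while 5.6 says that patients with loss of control may remain in the study. The reconciliation has to deal with this.

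**Conclusion.** The concern holds in a limited form. Protocol 5.6 conflicts with 8.2 and 8.3 on whether a loss-of-asthma-control event below the exacerbation criteria is an AE, and the SAP makes no use of the flag that 5.6 relies on. Such events may be counted at some sites and be missing from every planned safety output at others.

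The number of patients affected cannot be stated. The planned design would have put 77 to 81 of 147 patients under the rule, but the event rate, the use of discretion and the actual enrolment are all unknown. The conclusion about the SAP rests on its text alone and assumes no listing of the flag is specified in a document outside those reviewed. The point merits action because the remedy is cheap and the remaining analysis is about safety.

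**What to change.** 1. **SAP 4.12.2.** Add an output, for example: *Loss-of-asthma-control events flagged in the eCRF will be listed, and the number and percentage of patients with at least one such event will be summarised by treatment group, among patients in the Safety Set with comorbid asthma. The listing will show whether a matching AE was recorded.* First confirm that the flag is held as a data field.
2. **Before database lock.** Query each flagged event that has no matching AE, if the data management procedures do not already do so.
3. **Protocol 5.6 against 8.2 and 8.3.** The sponsor should decide and state whether a flagged event is an AE, and make the three sections agree. The decision must take account of the rule for related grade 2 or higher respiratory TEAEs in 5.7 and 8.7. Which rule should apply is for the sponsor and is not proposed here.

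The cost of items 1 and 2 is one output and some query work, using data that 5.6 already asks sites to flag. A few more disease-worsening terms may enter the TEAE tables. Item 3 needs ethics review as a protocol change (Protocol 11.4) and, after the decision to terminate, would do little for data already collected. Items 1 and 2 therefore carry most of the benefit.
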